Eligible patients will be identified prospectively utilizing a search paradigm previously described in Phase 1 of this project (Reference Protocol 2020E000255). Eligible patients will be selected from several sources, including the EHR and the Digital Care Transformation (DCT) cohorts, which are groups of patients who previously participated or are currently participating in medication titration for management of hypertension, hyperlipidemia, and HF with reduced ejection fraction. These patients will be screened for eligibility for inclusion in this program.

Inclusion Criteria: Patient is eligible if they meet ALL the following criteria.

- Type 2 diabetes currently on, or intolerant to, metformin (treated with diet, DPP4 inhibitor, sulfonylurea, pioglitazone, glinides, and/or basal insulin);
- Age 27-79 years;
- Hemoglobin A1c (HbA1c) 6.5-8.9% at the time of screening;
 - Participants whose baseline HbA1c after enrollment is 5.7-6.4% or 9.0-9.9% will remain in the program.
- At elevated cardiovascular and/or renal risk defined as any atherosclerotic cardiovascular disease (ASCVD)¹, estimated ASCVD risk $\geq 10\%$, HF, estimated glomerular filtration rate (eGFR) $< 60 \text{ mL/min}/1.73\text{m}^2$, urine albumin-to-creatinine ratio greater than 300 mg/g, or non-alcoholic fatty liver disease, and those aged 60 years or older with at least two of: tobacco use, dyslipidemia, hypertension, or abdominal obesity.

Exclusion Criteria: Patient is ineligible if they meet any ONE of the following criteria.

- Type 1 diabetes, type 3c diabetes (pancreatogenous), maturity onset diabetes of the young (MODY)
- Currently prescribed an SGLT2i or GLP1-RA;
- Currently prescribed basal and bolus insulin;
- History of diabetic ketoacidosis (DKA)
- History of hypoglycemia²;
- Frequent hypoglycemia (as defined as > 2 episodes in 1 week)², OR
- Prior liquid or solid organ transplant
- Limited life expectancy, difficulty managing one's medications, or any competing medical condition that, in the opinion of the investigator would diminish their ability to participate in the trial (i.e., active malignancy)
- Pregnancy, breastfeeding, or without adequate birth control utilization
- eGFR below $15 \text{ mL/min}/\text{m}^2$
- eGFR below $30 \text{ mL/min}/\text{m}^2$ with a history of pancreatitis

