Primary Outcome: By design, no patients will be on SGLT2i or GLP-1 RA therapy at baseline. We are excluding patients who are on the drugs of interest at baseline, so our primary outcome is the proportion of prescription therapy provided at 6 months. Our null hypothesis is that with we would expect with our education only (control) arm to increase rate of prescription from 0% to 5% based on secular trends and from 0% to 20% increase in SGLT2i or GLP-1 RA therapy in our intervention group utilizing navigators. 100 patients per arm will allow a 25% dropout rate to maintain power > 80% to maintain an alpha level of 0.05. As we are comparing the timing of education in the A/B allocated groups, we expect that our sample size will provide ~80% power to detect an absolute rate of prescription difference of 15% between our immediate titration and education prior to titration groups (i.e., at 3 months)

Secondary Outcomes: With a mean HbA1c of 7.2% and a standard deviation of 1%, to obtain 80% power to detect a 0.5% difference in HbA1c, we would need to enroll 63 patients per arm (preliminary data.) To account for dropout, (expecting 25% dropout) we will calculate $N1 = n/(1 - \text{dropout rate}) \Rightarrow 63/0.75 = 84$ patients per arm.

Data Management

Mass General Brigham will create a data collection instance within the patient-management application. All data will be collected and stored within the Mass General Brigham firewall in a HIPAA-compliant, encrypted server, key variables data will be randomly sampled and verified for accuracy in 40 patients representing 20% of the study population. Data will be stored for at least 5 years after project completion.

Data Analysis

We will utilize SAS software, version 9.4 (SAS Institute) to conduct our statistical analysis.

There will be ongoing quality checks of the data. Before final analysis, the data will be queried for outliers and missing data. The primary analysis will not impute any missing data though sensitivity analysis may use imputation methods such as last observation carried forward (LOCF).

Definition of Analysis Sets

For the Full Analysis Set (FAS) Patients will be included all patients enrolled (intention-to-treat analysis.)

The Per protocol Set (PPS) will include patients that did not drop out or become unreachable and completed the entire quality improvement program.

Statistical Methods

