For our primary outcome, the percent of patients on either an SGLT2i or GLP-1 RA from baseline to conclusion of the study at 6 months post-enrolment, we will perform a Chi-Square test to determine a difference in the terminal rates at the end of the study to determine treatment effects between groups.

We will develop a cumulative incidence curve displaying patients both prescribed and taking DRIVE medications for the duration of the program.

We will perform t-tests and Fisher's exact test for the baseline univariate analysis. As we will be utilizing A/B allocation there should be no bias or confounding at baseline, however if any significant differences are found, we will correct for these utilizing logistic regression. A/B allocation with 200 patients should cause any confounders to balance between the groups. We will also perform a longitudinal model for binary outcome at 6 months. For our co-secondary outcomes, the change in the HbA1c, and PAM from baseline to the end of the 6-month study, these will be analysed with a paired t-test and we will report a mean and standard deviation. A secondary analysis will be to conduct linear regression models with two variables (baseline HbA1c and baseline weight) to control for any confounders.

We will conduct our analysis via the intention-to-treat principle with two-sided type I error with an alpha of 0.05. For participants with missing outcome data, we will perform a sensitivity analysis with missing outcomes excluded or included as an event.

A priori sub-analyses will be performed based on zip code, baseline HbA1c, race, insurance status, and sex with a p-value threshold of 0.1 for these secondary analyses and we will account for multiple testing. A cox proportional hazards model will be performed to assess time-to-prescription between groups.

After the final data was reviewed, a series of subsequent hypotheses were identified for additional analysis. These analyses are, by definition, post hoc and, therefore, considered hypothesis-generating. A p-value of 0.05 will be considered significant without any correction for multiple comparisons.

Interim Analysis

N/A

Quality Control

Data will be collected from our EHR, the MGB Electronic Data Warehouse (EDW), and patients. Clinical laboratories within MGB system have laboratory certificates available upon request.

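### The SAP's 80% power for a 0.5-point between-arm HbA1c difference does not fit its own expected uptake of 5% v 20%; at that uptake, power is nearer 15% under an assumed 1-point fall per treated patient

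*SAP*

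**What the plan says.** The SAP, Study Sample Size, has two planning statements that bear on each other.

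- **Uptake (Primary Outcome).** Nobody is on either drug class at baseline. By 6 months the SAP expects 5% uptake in the control arm and 20% in the intervention arm, with 100 patients per arm and 25% dropout. It adds about 80% power to "detect an absolute rate of prescription difference of 15% between our immediate titration and education prior to titration groups", and ties that figure to 3 months.
- **HbA1c (Secondary Outcomes).** The inputs are given as "With a mean HbA1c of 7.2% and a standard deviation of 1%, to obtain 80% power to detect a 0.5% difference in HbA1c". The result is "we would need to enroll 63 patients per arm (preliminary data"), raised to 84 for dropout. The only source given is the reference to preliminary data, and 0.5 is not linked to the uptake figures.

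The SAP, Statistical Methods, analyses HbA1c change from baseline to 6 months as a co-secondary outcome with a paired t-test. The SAP's Exploratory Aim(s) list HbA1c as exploratory.

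**The concern.** Neither arm takes an SGLT2i or GLP-1 RA at baseline, and most patients in both arms are expected not to be on one at the end. The mean HbA1c difference between arms is an average over everyone, so the effect in the few extra treated patients is diluted by the many whose treatment with these drugs does not differ. A 0.5-point target takes no account of that dilution.

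What is at stake is interpretation. If the arms are compared on HbA1c and the result is not significant, a reader who has seen the 80% figure may take it as an adequately powered negative finding about education timing and glycaemia. On the plan's own uptake figures, the trial would have had little chance of detecting the difference it could expect.

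**Working it through.** **Inputs from the SAP.** HbA1c difference 0.5, SD 1, mean 7.2%, 80% power, 25% dropout, uptake 5% v 20%, 100 enrolled per arm (Study Sample Size); "two-sided type I error with an alpha of 0.05" (Statistical Methods).

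**Input not in either document.** The HbA1c fall per treated patient. I assume 1.0 point, with a range of 0.5 to 2.0.

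**1. Reproduce the stated figure.** For two independent means, n per arm = 2(1.960 + 0.842)² × SD²/difference² = 2 × 7.85 × 1/0.25 = 62.8, so 63. Then 63/0.75 = 84. Both match. A paired or one-sample formula gives 7.85/0.25 = 31.4, so 32. The 63 is therefore a between-arm figure, and the paired t-test in Statistical Methods does not explain it.

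**2. Effect needed per treated patient.** If the arm difference runs through uptake, mean difference = uptake difference × fall per treated patient.
- Expected uptake: 0.5/(0.20 − 0.05) = 3.33 points. A patient at the mean would go from 7.2% to 3.87%.
- Most generous reading, with all 20% counting and control uptake having no effect: 0.5/0.20 = 2.5 points, from 7.2% to 4.7%. The same 2.5 points would be needed for a 0.5-point mean change within the intervention arm if uptake were the only route.

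**3. Difference and power implied by planned uptake.** Evaluable n = 100 × 0.75 = 75 per arm. Standard error = 1 × √(2/75) = 0.163. Power = Φ(difference/0.163 − 1.96), ignoring the negligible chance of significance in the wrong direction.

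| Assumed fall per treated patient | Arm difference (× 0.15) | Power, 75 per arm |
|---|---|---|
| 0.5 | 0.075 | 6.7% |
| 1.0 | 0.15 | 14.9% |
| 2.0 | 0.30 | 45.1% |

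**4. What 75 per arm can detect.** At 80% power: 2.802 × 0.163 = 0.46 points.

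**5. What other routes would have to supply.** To reach 0.5, the remainder is 0.5 − 0.15 = 0.35 points between arms at a 1.0-point fall, or 0.5 − 0.30 = 0.20 at a 2.0-point fall.

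**6. Sensitivity to the SD.** A change score or baseline-adjusted analysis could have a smaller SD. With an assumed 0.6 in place of the SAP's 1, power at 75 per arm is about 12%, 33% and 86% for falls of 0.5, 1.0 and 2.0 points. Only the top of the assumed range passes 80%.

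**7. Time point.** The A/B 15-point figure is for 3 months, while HbA1c is read at 6. The education-first period is 2 months in the Protocol and 4 weeks in the SAP. The two need reconciling, but on either figure both groups are eligible for titration well before 6 months. The A/B uptake contrast when HbA1c is read may therefore be smaller than 15 points.

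**The case against.** The strongest reply is that nothing has been miscalculated. The SAP gives power to detect 0.5; it does not say that 0.5 is expected or that it derives from uptake. The A/B 15 points is likewise a difference to be detected. Uptake of the two drug classes is also not the only possible route to an HbA1c difference. The collaborative agreement covers other diabetes drugs, and deferring titration in one group defers those too. If the SAP's control arm is read literally as education only, that arm would have no such titration at all.

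Much of this stands. A reader might infer that the design cannot produce 0.5 points, or that the sample-size arithmetic is wrong. The documents support neither: other drugs and timing could add to the difference, and 63 and 84 are correct. A reader might also set the 3.87% against the Protocol's statement, "Participants whose baseline HbA1c after enrollment is 5.7-6.4% or 9.0-9.9% will remain in the program", and treat 5.7% as a floor. It is a limit on baseline values for staying in the program and does not bound HbA1c on treatment. Nor should power be quoted at 84 per arm, which is a number before dropout.

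The reply does not remove the mismatch. The 5% v 20% is stated as what the investigators expect, and the SAP neither names nor quantifies a route for the remaining 0.20 to 0.425 points (0.5 less 0.30 or 0.075).

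It is also fair that no between-arm HbA1c test is spelled out, and that HbA1c is exploratory in one place and co-secondary in another. That limits the harm, but the power statement itself is per arm and between arms, so such a comparison will be expected.

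**Conclusion.** The point holds as an inconsistency between two planning assumptions in one section. The 0.5-point target needs 3.3 points per extra treated patient (2.5 on the most generous reading) unless an unstated route contributes. At the planned uptake, the expected arm difference is about 0.15 points (0.075 to 0.30) and power about 15% (7% to 45%), against the stated 80%.

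This rests on SD 1 as in the SAP, 75 evaluable per arm, an HbA1c difference that runs through SGLT2i or GLP-1 RA uptake, and an assumed fall of 0.5 to 2.0 points per treated patient that neither document gives. A smaller SD would raise the power. A smaller uptake contrast at 6 months would lower it. Total enrolment is not in question, because 100 per arm already exceeds 84.

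**What to change.** In the SAP, Study Sample Size, Secondary Outcomes, do one of two things:

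- give the source of 0.5 and reconcile it with the uptake figures, naming any other route and how much it is expected to contribute; or
- keep 0.5 only as a detectable difference (about 0.46 at 80% power with 75 evaluable per arm), and add that planned uptake implies about 0.08 to 0.30 points, with power of about 7% to 45%, stating the assumed fall per treated patient and SD 1.

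In Statistical Methods, treat any between-arm HbA1c comparison as estimation, in line with its exploratory listing. Report it as a difference with a 95% CI, and state that a non-significant result is not evidence of equal glycaemic effect.

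The cost is wording only, with no added patients or data. The downside is that a stated power figure becomes less favourable.

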Roughly 50% of patients enrolled into this quality improvement program will be allocated into an “education first” pathway, which will provide 4 weeks of digital, paper, and customized video resources to explain the medical rationale and anticipatory guidance regarding diabetes care and therapeutics with proven benefit prior to becoming eligible for medical therapy prescription. In addition to looking at uptake and adherence, we will be measuring baseline and end-of-study Patient Activation Measures for each participant. Patient Activation Measures have been shown to correlate with increased self-care behaviors, medication adherence, and diabetes monitoring (11).

Primary Aim

The primary objective of this study is to create a remote diabetes management platform that compared to baseline, will improve initiation and adherence to contemporary guidelines regarding the use of glucose-lowering medications with cardiovascular and renal benefit for patients with type 2 diabetes and high cardiovascular and/or renal risk.

Secondary Aim(s)

- Evaluate optimal timing of patient education within the program. (measured as prescriptions by randomization arm, prescriptions at 2 months, and patients on therapy at end of study)
- Increase patient disease knowledge, activation, and engagement (as measured with short-form Patient Activation Measure)

Exploratory Aim(s)

Weight and HbA1c

We will compare age, socioeconomic demographics (where available), baseline characteristics and medical history, HbA1c, and demonstrate that they are evenly distributed in the population and between groups. We will report subgroup-specific rates if there are significant differences (e.g., evidence of heterogeneity).

Data Sources

Data will be collected from the electronic health record (HER) and directly from patients. All data will be stored in an encrypted, secure database within the Mass General Brigham firewall and using HIPAA-compliant applications.

Study Sample Size

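### Covariate adjustment of the primary comparison depends on baseline significance tests, and the SAP does not say which result is primary once a test is significant

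*SAP*

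**What the plan says.** The SAP's Statistical Methods section gives the primary test: "we will perform a Chi-Square test to determine a difference in the terminal rates at the end of the study". No covariate is named for it.

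The same section plans t-tests and Fisher's "exact test for the baseline univariate analysis". It expects A/B allocation to leave no baseline bias or confounding, but adds that "if any significant differences are found, we will correct for these utilizing logistic regression". The significance level for these tests is not given. The general statement is "two-sided type I error with an alpha of 0.05".

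The variables to be compared appear under Exploratory Aim(s): "We will compare age, socioeconomic demographics (where available), baseline characteristics and medical history, HbA1c". That list is open-ended, and the stated purpose is to "demonstrate that they are evenly distributed in the population and between groups".

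Fixed covariates are named only for the HbA1c and Patient Activation Measure outcomes, as a secondary analysis: "linear regression models with two variables (baseline HbA1c and baseline weight) to control for any confounders". A longitudinal model for the binary outcome is mentioned without covariates.

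Two passages bear on who is compared. The Protocol (Research Design and Methods) sends participants with a baseline HbA1c of 9.0-9.9% straight to immediate titration and keeps them out of the A/B testing. The SAP's Definition of Analysis Sets puts every enrolled patient in the Full Analysis Set.

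**The concern.** A baseline p-value measures imbalance between arms. It does not show whether a variable predicts prescription. If allocation works as the SAP expects, a significant baseline difference between the allocated arms is a chance event, and chance then decides whether the model is adjusted and for what. A variable unrelated to the outcome can enter, while a strong predictor just short of significance stays out. Nor can a non-significant test demonstrate even distribution, which is what the SAP wants from it.

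Two things are at stake. First, once the rule fires there are two candidate results, a difference in proportions and an odds ratio conditional on whichever variables were flagged, and the SAP does not rank them. Either could be reported as the planned analysis. Second, whatever precision is available from variables already collected is mostly given up, because the rule seldom selects the useful ones.

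**Working it through.** **1. The plan's own power.** Inputs from the SAP's Study Sample Size section: "education only (control) arm to increase rate of prescription from 0% to 5% based on secular trends", 20% in the intervention group, 100 per arm, 25% dropout (100 × 0.75 = 75 evaluable), two-sided alpha 0.05. The mean rate is 0.125.

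Power = Φ{[0.15√75 − 1.96√(2 × 0.125 × 0.875)] / √(0.05 × 0.95 + 0.20 × 0.80)} = Φ{(1.299 − 0.917) / 0.4555} = Φ(0.839) = 79.9%.

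Exact enumeration of the uncorrected chi-square gives 82.7%. The stated figure of more than 80% is reproduced, with no covariate needed.

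**2. How often the rule fires.** Assume k independent baseline tests at 0.05. P(at least one significant) = 1 − 0.95^k:

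- k = 5: 22.6%
- k = 10: 40.1%
- k = 15: 53.7%
- k = 20: 64.2%

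The SAP gives neither k nor the threshold. Any single variable is selected about 5% of the time, however prognostic it is (4.5% to 5.5% in the simulation below).

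**3. Power under the rule.** The simulation used 4,000 trials per row, 75 per arm, 5% versus 20%, and 10 independent normal baseline variables, of which one predicts the outcome. The rule was read as replacing the chi-square with the adjusted model whenever a test is significant. Adjusted models used a likelihood-ratio test. The prognostic strengths are assumptions. Monte Carlo error is √(0.83 × 0.17 / 4,000), about 0.6 points.

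| Log-odds per SD | Chi-square only | SAP rule | One fixed covariate | Fixed minus rule |
|---|---|---|---|---|
| 0 | 83.1% | 82.8% | 83.7% | 0.9 |
| 0.5 | 83.1% | 83.2% | 84.6% | 1.4 |
| 1.0 | 83.1% | 83.4% | 87.3% | 3.9 |
| 1.5 | 82.3% | 82.8% | 89.5% | 6.7 |

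The rule tracks the unadjusted test in every row. The first row shows that a little under 1 point of the last column is not a gain from prognosis.

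The gain depends on the event rates. At an assumed 40% versus 55% with 100 per arm, the rule gives 58.8%, 57.6% and 58.4% for strengths 0.5, 1.0 and 1.5. One fixed covariate gives 60.8%, 65.1% and 71.3%, a gain of about 2 to 13 points.

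**4. Type I error.** At 20% versus 20%, 75 per arm, strengths 0, 1.0 and 1.5:

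- chi-square: 5.1%, 4.8%, 4.8%
- SAP rule: 5.1%, 4.4%, 4.4%
- one fixed covariate: about 5.3% to 5.4%

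**5. What the ambiguity could do.** The rule and the chi-square disagree on significance in 1.7% to 2.9% of the trials in step 3, and in 0.72%, 1.18% and 1.40% of the null trials. If an analyst reported whichever was significant, the error would be (chi-square + rule + disagreement) / 2:

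- (5.12 + 5.10 + 0.72) / 2 = 5.5%
- (4.80 + 4.42 + 1.18) / 2 = 5.2%
- (4.82 + 4.38 + 1.40) / 2 = 5.3%

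That is less than half a point above the chi-square alone, for one fixed set of 10 variables and a fixed threshold. The SAP fixes neither.

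**6. Room for covariates.** Expected events are 75 × 0.05 + 75 × 0.20 = 18.75, or about 19. That supports one or two covariates, not a long list.

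**The case against.** The strongest defence is that the SAP names one primary test, the chi-square, and that the logistic regression can be read as a follow-up. A reader might infer that the logistic model replaces the chi-square and so changes the estimand. The text does not say so. What stands is that the status of the adjusted result is undefined.

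An unadjusted primary test is also a legitimate choice. The planned power is met without covariates, and the rule costs essentially nothing against the plain chi-square. This is correct. The efficiency argument is about a gain not taken, and its size is an assumption, because the documents name no factor shown to predict prescription.

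A reader might infer that every significant baseline difference must be chance. That holds only within the A/B-allocated patients. If participants with HbA1c 9.0-9.9% enter the comparison through a Full Analysis Set of all enrolled patients, an HbA1c imbalance is built in.

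A reader might also take the SAP's remark about hypotheses added after review of the final data as evidence that the primary analysis was chosen from the data. The remark concerns additional analyses that the SAP itself labels post hoc. It does raise a practical limit: if the between-arm comparison had already been run, a covariate list written now would not be pre-specified. The documents do not say whether it had.

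**Conclusion.** The point holds in a limited form. Baseline significance tests decide whether the comparison is adjusted and for which variables, and the SAP does not say which result is then primary. With independent tests at an assumed 0.05, the rule fires about 23%, 40% and 64% of the time for 5, 10 and 20 variables. Correlated variables or the conservatism of Fisher's test would change these figures.

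The rule recovers almost none of the precision that adjustment can offer. At the SAP's 5% and 20% rates with 75 evaluable per arm, fixed adjustment gains roughly 1 to 7 points of power for assumed log-odds of 0.5 to 1.5 per SD.

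The documents do not support a claim of inflated type I error or of an underpowered trial. The simulated error under the rule was 4.4% to 5.1%, and the power calculation reproduces. This should be corrected for clarity and efficiency. It does not threaten the validity of the chi-square result.

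**What to change.** - Delete the significance trigger, and describe baseline balance with summary statistics, without p-values.
- Name one primary analysis, restricted to the A/B-allocated patients. State that participants with HbA1c 9.0-9.9% assigned outside the A/B testing are not in it, and reconcile this with the Full Analysis Set definition.
- Fit a logistic model of the 6-month outcome on arm plus one or two fixed covariates already collected, whatever the baseline data show. Baseline HbA1c is a natural choice: it is already named for the secondary regression, and it is measured at screening, so few values should be missing. That matters because the primary analysis imputes nothing.
- Report a standardised risk difference with a 95% confidence interval, and keep the unadjusted chi-square as the supporting analysis.
- If the between-arm comparison has already been run, keep the chi-square primary and label the fixed-covariate model supportive.

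The cost is SAP wording, with no new data. The covariate list must be fixed before the comparison is run. With about 19 expected events, the adjusted model also needs a small-sample check, since its simulated type I error was slightly above that of the chi-square (about 5.3% to 5.4% against 4.8% to 5.1%).

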¹ ASCVD for this project is defined as history of myocardial infarction, angina, unstable angina, coronary revascularization, percutaneous coronary intervention, transient ischemic attack (TIA) stroke, peripheral artery disease, carotid artery disease ($> 50\%$ luminal obstruction)

² Hypoglycemia for this project is defined as a blood sugar $< 70 \text{ mg/dL}$

Patients recruited into the program will enter either 1) a gradual education period for 2 months followed by pharmacist and navigator-based medication titration, or 2) rapid education in conjunction with pharmacist and navigator-based medication titration via a Collaborative Drug Therapy Management (CDTM) algorithm designed to improve medical therapy for the treatment of type 2 diabetes with cardiorenal comorbidities. The CDTM will be approved by the BWH Pharmacy and Therapeutics committee. We will use A/B testing to optimize the timing of the educational program. Outcomes will include percentage of patients prescribed SGLT2i or GLP1-RA, percentage of prescriptions filled, HbA1c, change in the diabetes treatment satisfaction questionnaire short (DTSQs) score, and Patient Activation Measure (PAM) at enrollment and completion of the program.

Participants whose HbA1c rises to 9.0-9.9% following enrollment as part of their program baseline labs will automatically be assigned to immediate pharmacist and navigator-based medical titration and rapid education. As a result, participants with baseline HbA1c between 9.0-9.9% will remain in the program but will not be part of the A/B testing.

We will generate prototype software to guide DM medication changes based on patient-specific information and to longitudinally monitor each participant's progress through the algorithm and document

clinical and laboratory information. Basic patient demographic, laboratory, medication, and medical history data will be housed in a secure platform database for clinical management and communication.

Briefly describe study procedures. Include any local site restrictions, for example, “Subjects enrolled at Partners will not participate in the pharmacokinetic portion of the study.” Describe study endpoints.

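### HbA1c is sized as a between-arm comparison, but the SAP names only a paired t-test and a regression without an arm term, so its 80% power belongs to a test it does not specify

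*SAP*

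**What the plan says.** SAP, Study Sample Size (Secondary Outcomes), sizes HbA1c by arm: "to obtain 80% power to detect a 0.5% difference in HbA1c, we would need to enroll 63 patients per arm". The inputs are introduced as "With a mean HbA1c of 7.2% and a standard deviation of 1" (per cent), and 63 is inflated to 84 per arm for 25% dropout. Enrolment itself is set by the primary outcome in the same section: "100 patients per arm will allow a 25% dropout rate".

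SAP, Statistical Methods, gives two analyses that bear on HbA1c. The first, for outcomes labelled co-secondary, reads: "the change in the HbA1c, and PAM from baseline to the end of the 6-month study, these will be analysed with a paired t-test". Results are to be given as a mean and SD. A secondary analysis uses "linear regression models with two variables (baseline HbA1c and baseline weight) to control for any confounders". Comparisons between groups are written out only for the prescription outcomes: the chi-square test for the primary outcome and the Cox model for time to prescription.

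The role of HbA1c varies. Under Exploratory Aim(s) the entry is "Weight and HbA1c". The sample-size section treats HbA1c as secondary, and Statistical Methods calls it co-secondary.

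The Protocol (Research Design and Methods) limits who can enter an arm comparison: "participants with baseline HbA1c between 9.0-9.9% will remain in the program but will not be part of the A/B testing". It lists HbA1c as an outcome and gives no test for it.

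**The concern.** A sample size is tied to a test. A per-arm figure implies that the two education-timing arms will be compared on HbA1c, yet a paired t-test compares patients with themselves and gives no arm difference. Read literally, the regression has two baseline covariates and no treatment term.

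Both arms eventually receive pharmacist- and navigator-led titration, so HbA1c could fall in both. A highly significant paired result could then be set beside the stated 80% power and read as the 0.5-point arm difference the SAP sized for. It would show only change over time in the programme, with no control for secular change or regression to the mean. Because HbA1c is called both exploratory and co-secondary, a reader also cannot tell what weight such a result should carry.

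**Working it through.** **Inputs from the SAP.** Two-sided alpha 0.05 (Statistical Methods). Power 80%, difference 0.5, SD 1, dropout 25%, 100 enrolled per arm (Study Sample Size). Allocation is roughly 1:1.

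**Assumptions.** The SAP gives no correlation ρ between baseline and 6-month HbA1c, so 0.3, 0.5 and 0.7 are used. SD 1% is taken as the SD of the level. Completers: 100 × 0.75 = 75 per arm, 150 pooled.

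**1. Reproduce the SAP's figure.** Two independent means: n per arm = 2 × (1.96 + 0.8416)² × (1/0.5)² = 62.8, rounded up to 63. The t-based answer is 64, and power at 63 by the t distribution is 79.5%. Inflation: 63/0.75 = 84. The arithmetic is right, and it is a between-arm calculation.

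**2. Size the test the SAP names.** For a paired test the SD of change is √(2(1 − ρ)), and n = ((1.96 + 0.8416) × SD of change / 0.5)².

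| ρ | SD of change | n, normal | n, t-based | Power, 150 pooled |
|---|---|---|---|---|
| 0.3 | 1.183 | 44.0 | 46 | 99.93% |
| 0.5 | 1.000 | 31.4 | 34 | >99.99% |
| 0.7 | 0.775 | 18.8 | 21 | >99.99% |

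These are total patients, against 2 × 63 = 126 in the SAP. The power is for a 0.5-point fall over time and is the same whether or not the arms differ. The paired formula returns 63 only at ρ = 0, and then as a number of pairs rather than patients per arm.

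**3. Power for a true 0.5-point arm difference, 75 per arm.** ANCOVA residual SD is √(1 − ρ²). The change-score SD is as in step 2. SE = SD × √(2/75). The gain from baseline weight, and its one degree of freedom, are ignored.

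| ρ | ANCOVA SE | ANCOVA power | Change-score SE | Change-score power |
|---|---|---|---|---|
| 0.3 | 0.156 | 89% | 0.193 | 73% |
| 0.5 | 0.141 | 94% | 0.163 | 86% |
| 0.7 | 0.117 | 99% | 0.126 | 98% |

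If SD 1% is instead the SD of whatever quantity is analysed, power at 75 per arm is 86%.

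**4. How firm is 75?** At the stated dropout it is an upper figure. Enrolment is capped at 200 in all (Protocol, Consent Procedures), and patients with baseline HbA1c of 9.0–9.9% are enrolled but stand outside the A/B comparison.

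**The case against.** The strongest reply is that an arm term is implied. The regression is meant to control confounders, and a few sentences earlier the SAP speaks of confounders balancing between the groups. Confounding has meaning only for a contrast, so the model recommended here may be close to what was intended. That is a fair reading, and it makes this a gap in specification rather than proof that no comparison was planned. But the outcome of that regression is not named, the two listed variables omit arm, and the same section names the groups where it means to compare them.

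A second reply is that no stated aim needs a between-arm HbA1c result. The primary aim is framed against baseline, and the timing aim is measured by prescriptions and therapy. The sizing could therefore be restated as paired. That would remove the mismatch, but it would leave an uncontrolled before/after test that cannot compare the A/B arms, and it does not explain why HbA1c was sized per arm.

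Several limits stand:
- HbA1c does not set enrolment; the primary outcome does.
- Between-arm power is adequate with ANCOVA. The only figure below 80% is for unadjusted change scores at ρ = 0.3, which nobody proposes.
- Pooling the arms for the paired test is an assumption. Run in one arm of 75, paired power is about 95%, 99% and over 99.9% at the three correlations.
- SD 1% sits beside a mean level, so it most naturally describes the level.
- Secondary and co-secondary agree with each other; only the exploratory heading conflicts.

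**Conclusion.** The concern holds. The figure of 63 per arm is correct for a two-sample comparison, and the SAP names no such comparison for HbA1c, so the stated 80% power cannot be attached to the stated test. This conclusion rests on the text and on the reproduced sample size; it needs no assumed correlation.

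The illustrative sizes do depend on ρ of 0.3 to 0.7, SD 1% for the level, and 25% dropout. On that basis the paired test would detect a 0.5-point fall almost with certainty, while the comparison that was sized is feasible at 89% to 99% power once it is specified as ANCOVA. The primary prescription analysis is unaffected. This should be corrected, but it concerns a non-primary outcome. The SD definition is a minor clarification.

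**What to change.** - **Name the between-arm analysis.** Among A/B-allocated patients, regress 6-month HbA1c on arm, baseline HbA1c and baseline weight, and report the adjusted difference with a 95% CI. The covariates are those the SAP already lists.
- **Keep the paired change** as a description of the whole programme, not as evidence on education timing.
- **Give HbA1c one role** in the aims, sample-size and methods sections, and state whether SD 1% refers to the level or the change.
- **PAM.** The stated aim is an increase, which the paired test serves. The same model is needed only if an arm comparison is wanted.
- **Reconcile the timing.** The SAP measures to the end of the 6-month study, while the Protocol's Data and Safety Monitoring section counts HbA1c checks from the start of therapy, which the two arms reach at different times. For analysis, take available values near 6 months post-enrolment, within a stated window, for all allocated patients.
- **Date the addition.** Statistical Methods records that "After the final data was reviewed, a series of subsequent hypotheses were identified for additional analysis". If the model is added after data review, label it post hoc.

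The cost is SAP wording, one extra model on baseline values already collected, and a rule for choosing the 6-month value from available records. The downside is that the between-arm HbA1c result may have to be reported as post hoc.
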